## ABSTRACT

**Background:** Delirium is a common and serious complication of major surgery for older adults. Postoperative social and behavioral support (e.g., early mobilization, mealtime assistance) may reduce the incidence and impact of delirium, and these efforts are possible with proactive patient-care programs. This pilot trial tests the hypothesis that a multicomponent decision support system, which sends automated alerts and recommendations to patient-care programs and family members for high-risk patients, will improve the postoperative environment for neurocognitive and clinical recovery.

**Methods:** This will be a randomized, controlled factorial trial at a large academic medical center. High-risk, non-cardiac surgery patients ( $\geq 70$  years old) will be recruited. Patients will be allocated to a usual care group ( $n=15$ ), Hospital Elder Life Program (HELP)-based paging system ( $n=15$ ), family-based paging system ( $n=15$ ), or combined HELP- and family-based system ( $n=15$ ). The primary outcome will be the presence of delirium, defined by positive long-form Confusion Assessment Method screening. Secondary outcomes will include additional HELP- and family-based performance metrics along with various neurocognitive and clinical recovery measures. Exploratory outcomes include the incidence of positive family-based delirium assessments post-discharge, 36-item Short Form Survey, PROMIS Cognitive Function Abilities Subset 4a, and 30-day readmission rates.

**Ethics and dissemination:** This trial is pending approval by the University of Michigan Medical Institutional Review Board (IRBMED). Dissemination plans include presentation

at scientific conferences, publication in medical journals, and distribution via educational media.

**Trial registration:** [www.clinicaltrials.gov](https://www.clinicaltrials.gov), NCT04007523, registered on 7/3/2019.

## INTRODUCTION

Delirium is a distressing and common surgical complication, affecting approximately 20-50% of older surgical patients. Postoperative delirium is associated with increased mortality, cognitive and functional decline, and healthcare resource utilization. Of the diverse prevention strategies that have been tested with variable success, one notable proactive patient-care program, the Hospital Elder Life Program (HELP), has been shown to reduce delirium incidence through social and behavioral interventions (e.g., mealtime assistance, support with visual/hearing aids). However, substantial resources are needed for program sustainment, and delirium still persists in high-risk patients. In 2018, we found that <50% of surgical patients ≥70 years old at Michigan Medicine were officially enrolled in the program by the end of the second postoperative day. Furthermore, the average length of cumulative therapeutic activity was only 10 minutes across the first three postoperative days. This is pertinent given that the peak incidence of postoperative delirium occurs within the first 48 hours. As such, complementary strategies that improve patient triage and support may lead to earlier identification and therapeutic intervention for high-risk patients.

Clinical decision support systems can serve as a candidate strategy for mitigating delirium risk. Such systems provide targeted patient- and disease-specific information, presented in a timely manner, for improving healthcare quality. In the context of delirium, automated pages could be sent to supportive healthcare services, such as HELP, along with family members and caretakers, with alerts and targeted recommendations. An alert page could be sent to HELP program officials on the first

postoperative morning requesting early evaluation and enhanced treatment protocols. This may improve high-risk patient triage, early resource allocation, and cumulative therapeutic time spent with patients. A similar paging system could be implemented for family members and caretakers, as family-based interventions may provide additional support for patients at risk for delirium. Feasibility has been demonstrated with family-based protocols for hospitalized medical patients, with therapeutic focus on re-orientation, visual and hearing aid assistance, and conversational stimulation. Similar protocols could be adapted for surgical patients, as surgery is generally a predictable event (and thus may be amenable to familial planning), and family support may correlate with overall postoperative recovery. A recent systematic review also demonstrated that *family-performed* delirium screens demonstrated improved psychometrics compared to *family-informed* delirium screens (i.e., those not performed by family members). Thus, family members and caretakers could be recruited to actively participate in postoperative recovery by performing family-based delirium assessments and implementing therapeutic protocols. An electronic, paging-based alerting system could provide family members with reminders and alerts for conducting such a program.

The premise of this pilot proposal is thus formed by the above considerations: preliminary evidence that suggests (1) suboptimal delirium prevention resource utilization and (2) the potential role for a clinical decision support system involving HELP and family members. The primary objectives of this study are to determine whether pager-based clinical decision support systems bolster HELP- and family-based

therapeutic activities. A secondary objective will be to identify facilitators and barriers to delivering therapeutic interventions for both HELP and family members. Overall, this pilot trial will test the hypothesis that a multicomponent decision support system will improve the postoperative environment for neurocognitive and clinical recovery in older, high-risk surgical patients.

## **METHODS AND ANALYSIS**

[figure not shown]
### **Study Overview and Design**

This is a single-center, randomized, factorial pilot trial at Michigan Medicine (Ann Arbor MI, USA). Approval was obtained from the University of Michigan Medical School Institutional Review Board (HUM00165251), and the trial has been registered at [www.clinicaltrials.gov](http://www.clinicaltrials.gov) (NCT04007523). This protocol is also compliant with the Consolidated Standards of Reporting Trials (CONSORT) extension for pilot and feasibility trials and the Standard Protocol Items: Recommendations for Interventional Trials (SPIRIT) Guidelines. Lastly, all study team members are certified in Good Clinical Practice.

After enrollment, patients (n=60) will be allocated (1:1:1:1), via block-randomization, stratified by gender, to one of four groups: usual care (n=15), HELP-based paging system (n=15), family-based paging system (n=15), or both HELP- and family-based paging system (n=15) (Figure 1). The randomization code will be created by the biostatistician (AT) and concealed from the rest of the research team. On the morning of surgery, allocation assignments will be delivered via sequentially numbered, opaque, sealed envelopes to unblinded research team members who will initiate arm-specific operations. The support systems will consist of automated pager alerts to the HELP program and/or family members and caretakers, depending on group allocation, for providing additional delirium evaluation and therapeutic prevention activities (see Interventions – Clinical Decision Support Paging System). Family members in the intervention group will also be provided with preoperative education on delirium and

training in the Family Confusion Assessment Method (FAM-CAM) instrument.

Although it will not be possible to blind patients and family members to family-based interventions, study team members will remain blinded to group allocation during daily assessments. Study flow is illustrated in Figure 1.

**Figure 1.** CONSORT study flow diagram. HELP = Hospital Elder Life program; CAM = Confusion

Assessment Method, LTAC = Long-Term Acute Care

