## **Statistical Analysis**

### *Sample Size and Power*

Given its fluctuating and recurrent nature, delirium presence will be primarily assessed over time with logistic generalized estimating equation models as we have done previously. In brief, time and group will serve as fixed factors, and a group by time interaction term will be included. Interaction terms will be removed from models if no significant interaction effect is observed. These models allow for longitudinal data analysis in the setting of incomplete and missing data. Group models will be constructed individually with the control group serving as a reference. Power calculations were then conducted with generalized estimating equations for the time-averaged difference between two groups (i.e., control group and intervention group, either HELP- or family-based support) in a repeated-measures design with the binary outcome of delirium. Accounting for six equally spaced measurements (twice daily delirium assessments for

the first three postoperative days), with an autoregressive correlation structure (baseline correlation 0.3) and linear missing data structure, a total sample size of 60 patients (n=30 in each intervention group) will provide >80% power to detect a difference in proportions of 15% (approximate Cohen's effect size difference of 0.9) for experiencing an episode of delirium between groups (assuming a baseline proportion of 20% in the control group) with  $\alpha=0.05$ . Power analysis was conducted using PASS 16 (PASS 2019 Power Analysis and Sample Size Software [2019]. NCSS, LLC. Kaysville, Utah, USA, [ncss.com/software/pass](http://ncss.com/software/pass)). As an exploratory analysis, the interaction between HELP- and family-based support groups will be assessed using a generalized estimating equations model.

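### Randomisation is stratified by gender but the primary delirium GEE has no gender term, so its test is mildly conservative if gender predicts delirium (minor)

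*Combined protocol and SAP*

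**What the plan says.** Study Overview and Design assigns 60 patients in equal numbers "via block-randomization, stratified by gender, to one of four groups". Gender is the only stratification factor named. Table 4 under Ethical Considerations repeats that randomisation is stratified and blocked.

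Sample Size and Power describes the primary analysis: "delirium presence will be primarily assessed over time with logistic generalized estimating equation models". On the terms of the model it says "time and group will serve as fixed factors, and a group by time interaction term will be included", and then "Interaction terms will be removed from models if no significant interaction effect is observed". On the comparisons it says "Group models will be constructed individually with the control group serving as a reference".

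Gender does not appear in that description, in the power calculation, in the exploratory HELP-by-family model, in the fidelity tests or in Sensitivity Analysis and Missing Data. No covariate adjustment is specified anywhere. The variance estimator for the GEE is not named either.

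**The concern.** Stratified allocation forces the arms to have nearly the same gender mix. If delirium risk differs by gender, the arm difference then varies less from one randomisation to the next than it would under simple randomisation. A model with only time and group cannot see this. It leaves the between-gender variation in its error term and reports a standard error that is too large. The group-by-time term does not help, because it carries no gender information.

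At stake are a test that runs below its nominal level, intervals slightly too wide, and a small loss of power in a small trial. Strengths and Limitations says that the pilot will supply effect sizes for later power calculations, so overstated standard errors could carry into that planning.

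**Working it through.** **Inputs from the documents (Sample Size and Power; Study Overview and Design).** Six assessments per patient, AR(1) correlation 0.3, 30 v 30, control proportion 20%, difference 15 points (taken as 20% v 5%), alpha 0.05 (taken as two-sided), gender-stratified blocks.

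**Assumed, because the documents do not say.** A gender–delirium odds ratio from 1 to 5, half the patients of each gender, and no missing data in the simulations.

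**Step 1: the plan's own figure.** The variance factor for the mean of six AR(1) measures is [6 + 2(5×0.3 + 4×0.3² + 3×0.3³ + 2×0.3⁴ + 0.3⁵)]/36 = 9.919/36 = 0.2755.

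- Log odds ratio: ln(0.25) − ln(0.05/0.95) = 1.558.
- SE = √[(0.2755/30)(1/0.16 + 1/0.0475)] = 0.501.
- Power = Φ(1.558/0.501 − 1.96) = Φ(1.15) = 87.5%.

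If missingness rises linearly to 20% or 50% at the last visit, this becomes 85.3% or 80.7%. The stated power above 80% is reproduced, and gender plays no part in it.

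**Step 2: size of the effect by hand, under the null at 20%.** Let p₀ and p₁ be the two gender-specific risks, averaging 20%.

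- Between-gender variance: τ² = ¼(p₁ − p₀)².
- Within-gender variance of a patient's mean: σ² = 0.2755 × average of p(1 − p).
- With exact balance, the true variance of an arm mean is proportional to σ², but the model without gender reports σ² + τ². So SE/SD = √(1 + τ²/σ²), and null rejection = 2[1 − Φ(1.96 × SE/SD)].

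| Gender OR | p₀, p₁ | τ² | σ² | SE/SD | Null rejection |
|---|---|---|---|---|---|
| 1 | 0.200, 0.200 | 0 | 0.0441 | 1.000 | 5.0% |
| 2 | 0.146, 0.254 | 0.0030 | 0.0433 | 1.034 | 4.3% |
| 3 | 0.117, 0.283 | 0.0070 | 0.0422 | 1.080 | 3.4% |
| 5 | 0.084, 0.316 | 0.0134 | 0.0404 | 1.154 | 2.4% |

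**Step 3: simulation.** Gender-stratified blocks, 30 v 30, six correlated binary measures, logistic GEE with time and group, independence working correlation and uncorrected sandwich SE, 6000 replicates per setting. The Monte Carlo error at 5% is √(0.05×0.95/6000) = 0.3 points.

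| Gender OR | Mean SE v true SD, no gender term | Null rejection: without → with gender | Power, 20% v 5%: without → with gender |
|---|---|---|---|
| 1 | 0.360 v 0.361 | 5.1% → 5.1% | 92.6% → 92.4% |
| 2 | 0.368 v 0.362 | 4.3% → 4.8% | 92.3% → 92.8% |
| 3 | 0.378 v 0.356 | 3.7% → 5.3% | 91.5% → 92.7% |
| 5 | 0.395 v 0.346 | 2.5% → 5.0% | 90.3% → 93.2% |

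The reported SE exceeds the true SD by about 6% at an odds ratio of 3 (0.378/0.356 = 1.062) and 14% at 5 (0.395/0.346 = 1.142). With gender in the model the two agree (0.370 v 0.373 and 0.379 v 0.378). A second simulation with 3000 replicates gave unadjusted null rejection of 4.1% at 3 and 2.8% at 5. The hand calculation is a little more extreme because it assumes exact balance. Simulated power is higher than the formula's 87.5%, so only the differences between columns should be used.

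**Step 4: the smaller comparison.** If each arm is compared separately with control, the comparison is 15 v 15. At an odds ratio of 3, null rejection is 3.9% without gender and 5.2% with it.

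**The case against.** The strongest reply has four parts.

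1. **No evidence that gender is prognostic here.** The documents give no gender–delirium association, so every odds ratio above 1 is an assumption. This stands. The loss is conditional, and at an odds ratio of 2 or less it is too small to matter.

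2. **The remedy has its own small-sample cost.** A further simulation (4000 replicates, uncorrected sandwich SE, exact balance within gender, gender odds ratio 1.5–3, 50% or 65% of one gender) gave these null rejection rates: at 30 v 30, 4.2–6.1% unadjusted and 5.5–6.5% adjusted; at 15 v 15, 4.6–6.9% and 6.7–7.7%. At 15 v 15 with 20% v 5%, an odds ratio of 3 and 65% of one gender, model failures rose from 3.0% to 8.3%, and power did not improve (64.0% v 63.5%). These rates are higher than the adjusted rates under working, so the result depends on the simulation setting and the variance method. This also stands: part of the apparent power gain may come from a looser test, and gender should not go in without a variance correction and a fallback.

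3. **It is a pilot, and the model is described only briefly.** The plan defers rigorous analysis to a later trial, and one to three power points would change no decision here. That limits severity. But a brief description that omits gender leaves its inclusion open until the data are seen, and settling it now costs one line.

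4. **The odds ratio changes meaning**, from marginal to gender-conditional. True; the plan should say so.

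A reader might also want gender in the fidelity comparisons. The documents do not support treating that as the same small change. Those comparisons use t, Mann-Whitney, chi-squared and Fisher tests, which take no covariate, so the methods would have to be replaced, and no calculation here shows a benefit.

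**Conclusion.** The mismatch is real and minor. The design balances on gender, and no specified model includes it. If gender is strongly prognostic, the primary test at 30 v 30 rejects a true null about 4% of the time at an assumed odds ratio of 3 and 2.5–3% at 5, and about 1 to 3 power points are lost. At 2 or less the effect is small, and at 1 there is none. These sizes rest on the assumed odds ratios and the simulation settings given above.

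A reader might infer that the primary result would be biased, that false positives would rise, or that the power statement fails. None of these follows. Stratification keeps the arms comparable on gender. Leaving gender out makes the test conservative. The excess rejection seen in some small-sample runs reflects the uncorrected sandwich variance and is larger with gender in the model. The power above 80% reproduces without reference to gender. Nor can it be said flatly that power is lost: that depends on an association that the documents do not report.

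**What to change.** In Statistical Analysis, Sample Size and Power:

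- Add gender as a fixed covariate to the primary delirium GEE and to the exploratory HELP-by-family GEE.
- Name a small-sample-corrected sandwich variance (for example Mancl–DeRouen or Kauermann–Carroll). The simulations above used the uncorrected form, so the chosen correction should be checked at the planned group sizes.
- State that the unadjusted model will be used if the adjusted model does not converge.
- State that the reported odds ratio is conditional on gender, and give a standardised risk difference beside it.

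Leave the fidelity tests as they are.

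The cost is one model term and a few sentences, with no new data, because gender must already be recorded to randomise. The downsides are slightly more analysis work and an odds ratio that is conditional rather than marginal.

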## **Recruitment**

Participants will be screened and recruited at preoperative clinics, preoperative holding areas, and surgical wards (if patients are pre-admitted). Written informed consent will be obtained from all participants prior to scheduled surgery. Written informed consent will also be obtained from a designated family member of caretaker for each participant, given the family-based nature of interventions being tested. Supplemental recruitment materials will be distributed in conjunction with the Michigan Institute for Clinical and Health Research, the NIH-funded Clinical and Translational Science Award institute at the University of Michigan. Specifically, recruitment fliers will be posted throughout preoperative clinics, and informative postcards will be sent to potentially eligible patients preoperatively.

## **Eligibility criteria**

Eligibility criteria will reflect the pragmatic nature of the trial balanced with the aim of recruiting patients at high risk for postoperative delirium. Based on a validated geriatric assessment tool for predicting postoperative complications, surgical patients  $\geq 70$  years of age presenting for major inpatient surgery demonstrated a seven-fold increased risk of major complications compared to minor surgery. Inclusion criteria will thus reflect such patients, and overall eligibility criteria are outlined below:

### Inclusion criteria:

- Age  $\geq 70$  years of age

- Major non-cardiac, non-intracranial neurologic, and non-major vascular surgery, as defined by work-related value units suggestive of high surgical complexity.
- Anticipated length of hospital stay at least 72 hours
- At least one family member, or caretaker, available on each of the three first postoperative days for trial operations

Exclusion criteria:

- Emergency surgery
- Severe cognitive impairment (precluding ability to perform delirium assessments)
- Planned post-operative ICU admission (HELP unavailable in the ICU)
- Non-English speaking

**Interventions – Clinical Decision Support Paging System**

This proposal will build upon previous decision support systems launched by our department for reducing intraoperative awareness and delivering protective lung ventilation strategies. For participants randomized to the HELP-based support system, a single page will be sent to the on-call HELP staff during the first postoperative morning as the team begins ward rounds (Table 1). The page will request an enhanced treatment protocol, which includes HELP visitations three times daily. Therapeutic treatment will be administered during each visit per program protocols, which generally includes cognitive engagement, mealtime assistance, mobility and range of motion exercises, and assistance with visual and hearing aids. During the final evening visit, a sleep protocol will be implemented. For this protocol, HELP officials offer sleep and relaxation exercises, relaxation massages, and warm milk and/or tea.

For participants randomized to the family-based system, family members (or caretakers) will receive preoperative education on delirium (including an educational video), a folder with an informational flyer and therapeutic activities checklists, and FAM-CAM training. Suggested therapeutic activities include daily assistance with visual and hearing aids, providing assistance with drinking and mealtime assistance, handwashing, re-orientation to time and place, and cognitive stimulation activities (Supplementary Appendix). Lastly, family members will also receive a pager, and automated pages will be sent twice daily with reminders to perform these activities (Table 1). Completion of activities will then be logged daily in conjunction with unblinded members of the research team. Study activities for each group are listed in Table 2.

Days	Timing	Alphanumeric Paging Message
HELP-Based Paging System		
Postoperative day 1	Morning – 9:00 AM	Patient LAST NAME, FIRST NAME, MRN is at high-risk for postoperative delirium. Please evaluate patient as soon as possible and enroll in the enhanced treatment protocol.
Family-Based Paging System		
Postoperative days 1-3	Morning – 9:00 AM	Good morning! please complete the morning tasks listed in your folder (Morning Tasks 9:00 AM). The stimulating activity can then be performed anytime during the day. Call [contact] with questions or concerns.
Postoperative days 1-3	Afternoon – 3:00PM	Good afternoon! please complete the afternoon tasks in your folder (Afternoon Tasks – 3:00 PM). After these are complete, perform a FAM-CAM. Make sure to also complete a stimulating activity today. Call [contact] with any questions.

**Table 1.** Real-time clinical decision support – family paging system. FAM-CAM = Family Confusion

Assessment Method

Usual Care Group (n=15)	HELP-Based System (n=15)	Family-Based System (n=15)	Combined Systems (n=15)
Preoperative Phase	Preoperative Phase	Preoperative Phase	Preoperative Phase
Standard Care	Standard Care	Preoperative delirium education, materials, FAM-CAM training	Preoperative delirium education, materials, FAM-CAM training
Intraoperative Phase	Intraoperative Phase	Intraoperative Phase	Intraoperative Phase
Standard Care	Standard Care	Standard Care	Standard Care
Postoperative Care	Postoperative Care	Postoperative Care	Postoperative Care
HELP evaluation and treatment per ward routine	HELP pager alerts	Daily family pager alerts	HELP pager alerts and associated activities
Standard care otherwise	
 
• Early evaluation request
 
• Enhanced therapeutic protocol request
 
	
 
• FAM-CAM reminders
 
• Reminders for behavioral/social support and prevention activities
 
	Family pager alerts and associated activities

**Table 2.** Participants will be randomized to one of four groups: usual care, HELP-based paging support, family-based paging support (automated pages for the first three postoperative days), or combined HELP- and family-based paging support. HELP = Hospital Elder Life Program; FAM-CAM = Family Confusion Assessment Method.

